Remote CO Assessment. At the final treatment session, participants will be provided with a carbon monoxide (CO) monitor and trained to submit a breath CO sample via REDCap at 24-hours post-QA (i.e., upon waking on Day 30 for the short baseline condition or Day 44 for the long baseline condition). This procedure will be used to conduct remote bioverification of smoking status. Developed by [name], a study collaborator at the University of Florida, 38-43 this method has demonstrated feasibility among a variety of populations, including older adults. We will provide each participant with written instructions and contact information for the research team should they have any questions about the CO monitor.

End-of-Treatment Session. Participants will return for an end-of-treatment (EOT) study assessment approximately one week following their target quit date. At this assessment, participants will complete a final set of questionnaire measures on smoking-related variables, treatment implementation variables, and the behavioral target of smoking for affect regulation, described below. Participants will also return the CO monitor device and receive compensation for all completed ED assessments.

Behavioral Treatment Components. Treatment components are cognitive-behavioral strategies

adapted from the Unified Protocol (UP) for the Transdiagnostic Treatment of Emotional Disorders. For the current study, we will evaluate only the three modules that have been shown to reduce reliance on smoking for affect regulation before a QA

and provide skills to cope with acute nicotine withdrawal after quitting: Mindfulness, Interoceptive Exposure, and Behavioral Activation (described below).

Behavioral counseling strategies for smoking cessation, drawn from current US Public Health Service guidelines, are incorporated in each treatment module. All participants will be provided with the American Lung Association Freedom from Smoking guide to aid in their quit attempt.

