#### Measures.

Psychological Factors. Anhedonia will be assessed with the Environmental Reward Observation Scale (EROS), which measures amount of pleasure experienced from daily activities. Anxiety sensitivity will be assessed with the Anxiety Sensitivity Index (ASI-3), a measure of tendency to fear body sensations. Distress intolerance will be assessed with the Distress Tolerance Scale (DTS), which assesses perceived tolerance of negative physical or emotional states.

Smoking-Related Variables. We will administer a Smoking History Questionnaire to assess baseline smoking characteristics. We will administer validated PROMIS measures of nicotine dependence and smoking coping expectancies. We will administer the Cessation Fatigue Scale, a measure of perceived tiredness of

trying to quit smoking. Smoking status will be assessed with timeline follow-back methods, and will be supplemented with an assessment of expired carbon monoxide (CO) at inperson assessment sessions to provide bioverification of smoking status. Lastly, an outside-study treatment review will be conducted to identify any pharmacotherapy or behavioral therapy for smoking cessation received outside of the study.

COPD-Related Variables. We will conduct a chart review to identify participants' most recent sixminute walk test and spirometry (FEV1) values prior to COPD hospitalization. The chart review will also be used to supplement participants' self-report of any hospitalization for COPD at the time of the 3-month follow-up assessment. COPD symptom impact will be assessed with the COPD assessment test (CAT), an 8-item questionnaire measuring the global impact of dyspnea on health status. PROMIS measures will be used to assess task avoidance and emotional response to dyspnea symptoms.

Table 2. Phase 2 Study Measures	idy Measures Timepoint Assesse		
,	Baseline	Treatment Sessions	End-of- treatment
Demographic Questionnaire	X		
Contact Form	X		
Psychological Factors			
Anxiety Sensitivity Index	X		X
Environmental Reward Observation Scale	X		X
Distress Tolerance Scale	X		X
Smoking-Related Measures			
Smoking Motives Questionnaire-Revised	X		
Smoking History Questionnaire	X		
PROMIS-Nicotine Dependence	X		X
PROMIS-Coping Expectancies	X		X
Cessation Fatigue Scale	X		X
Smoking timeline follow-back	X		X
CO assessment	X	X	X
Outside-study treatment review	X	X	X

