COPD-Related Measures			
Six-minute walk test	X		
Spirometry (FEV1)	X		
Charlson Comorbidity Index	X		
COPD Assessment Test	X		X
PROMIS- Dyspnea Task Avoidance	X		X
PROMIS- Dyspnea Emotional Response	X		X
Depression and Anxiety Measures			
PROMIS- Depression short form	X		X
PROMIS- Anxiety short form	X		X
Treatment-Related Measures			
Freiberg Mindfulness Inventory	X	X	X
Avoidance and Inflexibility Scale	X	X	X
Behavioral Activation for Depression			
Scale	X	X	X

Depression and Anxiety Symptoms. PROMIS short forms will be used to assess past-7 day depression and anxiety symptoms. 

Treatment Implementation. To assess treatment implementation, participants will complete process measures at each treatment session assessing skill acquisition specific to each module (i.e., Freiberg Mindfulness Inventory,  Avoidance and Inflexibility Scale,  and Behavioral Activation for Depression Scale,  respectively).

Behavioral Target. The behavioral target will be smoking for affect regulation, as measured by 13 items from the Smoking Motives Questionnaire-Revised (SMQ-R).  $^{33,60}$  Items are adapted from a measure of drinking motives and have been validated to assess coping motives across classes of substance use.  $^{32,60,61}$  SMQ-R items can be modified to assess within-subject, state-like motives for use via ecological momentary assessment  $^{62}$  and have demonstrated good internal consistency.  $^{63}$  Further, these items are sensitive to treatment-related change (i.e., reduced as a function of a brief behavioral intervention) $^{64,65}$  and specifically related to reductions in substance use and associated problems, above and beyond non-affective motives.  $^{64,65}$  Responses are scored from 0 (not at all) to 100 (extremely) and averaged to index the overall tendency to smoke for affect regulation. Threshold of clinically-significant change is set at  $\geq 30\%$ , as this change magnitude was associated with substance use outcomes in prior studies.  $^{64,65}$  Specific items which index smoking for distress termination (e.g., "To turn off negative thoughts about myself"), anxiety reduction (e.g., "Because it helped me when I was feeling nervous"), and pleasure enhancement motives (e.g., "To help me feel more positive about things in my life") will be examined separately in follow-up exploratory analyses.

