Clinical Endpoint. The clinical endpoint will be achievement of 24-hour smoking abstinence at end-of-treatment, as verified by CO < 5 ppm,  $^{66,67}$  for at least 60% of participants (i.e., 3 of the 5 participants receiving each module), as this is consistent with rates of initial abstinence achieved by established smoking cessation treatments.  $^{68,69}$  We chose this endpoint because it is highly sensitive to treatment effects,  $^{70}$  strongly predictive of long-term abstinence,  $^{69,71}$  and especially relevant for smokers with elevated psychological risk factors who are vulnerable to early lapse.  $^{72,73}$ 

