## 14.0 Confidentiality and Data Management:

### **Data Management**

Sources of data include a) consent forms, b) self-report questionnaires, c) expired CO values, d) digital audio recordings, and e) chart review variables. Data will be stored for a minimum of 7 years after study completion on a secure Rush University network drive and in a double-locked office suite within the Department of Preventive Medicine. At the conclusion of the study, all data will be stripped of identifiers and archived for future analysis.

Procedures to secure the data include training and ongoing supervision of study staff; use of an encrypted, digital recording device; storage of all private health information on a secure network drive; and the use of numeric code identifiers. Digital audio recordings will be identified by numeric code only, and submitted to the transcription service via their secure, cloud-based Exavault server. [name] will be responsible for data and safety monitoring activities. She will provide oversight of the maintenance of patient confidentiality and will report any breaches of confidentiality to the IRB. She will report any changes to the study's risk/benefit ratio to the IRB. Only the study investigators will have access to the master list of participants' names and codes. All co-investigators and study personnel have completed CITI training in human subjects research.

All questionnaire measures will be completed using REDCap data management software, which allows real-time data quality control measures (e.g., requiring fields to be completed, restricting ranges of acceptable values). We will also complete data quality checks by automatically setting each form status to 'Unverified' upon initial entry. Study staff will click on each unverified record, check for data quality and completeness, and select either 'Complete' or 'Incomplete.' They will then lock the form to prevent further changes, with administrative privileges set to unlock forms only for the study investigators. REDCap data will be downloaded and backed up on the secure Rush University network drive on an ongoing, monthly basis.

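### Could a post-quit score for smoking for affect regulation merge the two Phase 2 selection milestones?

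*Combined protocol and SAP*

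**What the plan says.** Section 4.0 defines the behavioral target as 13 items from the SMQ-R: "Responses are scored from 0 (not at all) to 100 (extremely) and averaged to index the overall tendency to smoke for affect regulation". Aim 2 and the Behavioral Target paragraph set clinically significant change at 30% or more and justify that size by citation. Neither says which score is compared with which.

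Three parts of section 4.0 bear on when the target is measured:

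- The text describes an "end-of-treatment (EOT) study assessment approximately one week following their target quit date" at which "participants will complete a final set of questionnaire measures on smoking-related variables, treatment implementation variables, and the behavioral target of smoking for affect regulation".
- Table 2 has columns for baseline, treatment sessions and end of treatment. The row for the "Smoking Motives Questionnaire-Revised" is marked at baseline only, while neighbouring smoking measures are also marked at end of treatment.
- The Electronic Diary paragraph schedules nightly entries through the baseline and treatment phases, about 29 (short baseline) or 43 (long baseline). It does not list the items asked.

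The other milestone is "achievement of 24-hour smoking abstinence at end-of-treatment", verified by carbon monoxide (CO), in at least 3 of the 5 participants given each module. Under Phase 2 Data Analyses (section 14.0), a component goes into the Phase 3 manual only if it shows the hypothesized effects on both milestones. The same paragraph adds a rule based on the effect size d: all three components if every d is at least 0.5, otherwise the two largest.

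**The concern.** The 30% milestone helps decide which components go forward, yet its data source is not named. The one explicit statement about collecting the target after baseline places it after the quit date.

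That timing would matter. The items ask for reasons for smoking, and one example is in the past tense: "Because it helped me when I was feeling nervous". The protocol does not say how someone who has not smoked should answer. It does say that REDCap allows "real-time data quality control measures (e.g., requiring fields to be completed, restricting ranges of acceptable values", so a number may be required, and 0 would be a natural choice. A fall in the score would then partly restate abstinence. It also could not show the intended order of effects, since the modules were chosen because they "reduce reliance on smoking for affect regulation before a QA" (a quit attempt). The target milestone could stop screening out components that help people quit for a day without changing why they smoke.

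**Working it through.** **1. The plan's own figures.** 15 participants over 3 modules gives 5 per module, and 3/5 = 60%, as stated. The schedule also reproduces:

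| | Short baseline | Long baseline |
|---|---|---|
| Baseline days | 7 | 21 |
| Final session (baseline + 21) | Day 28 | Day 42 |
| Quit date (+1) | Day 29 | Day 43 |
| CO sample (+2) | Day 30, as stated | Day 44, as stated |
| Diary entries, Day 1 to quit date | 29, as stated | 43, as stated |
| End-of-treatment visit (quit + 7) | Day 36 (stated: about 35) | Day 50 (stated: about 50) |

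The diary therefore has at most one entry on the quit date and none after it. If the five-week session window is used, the quit date moves with the final session, to Day 36 or 50. That equals the maximum number of paid entries (36 or 50).

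**2. Which source fits the written analysis.** The analysis paragraph specifies change over the course of treatment through visual interpretation and non-overlap, then d relative to baseline. Each needs a series in both phases. One end-of-treatment score gives no non-overlap measure and no phase-based d. The multiple-baseline design looks for change that coincides with the start of a module, which also needs a series. The Behavioral Target paragraph says the items can be adapted for momentary assessment. Table 2 has no diary column, so a blank there does not show that the diary omits the items. Its single baseline mark fits the eligibility rule in section 3.0 (coping subscale at least 30).

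**3. Size if the end-of-treatment score did count.** Suppose *a* of 5 people are smoke-free and score 0, the others are unchanged, and baselines are equal. The fall in the mean is *a*/5: 20%, 40% or 60% for *a* = 1, 2 or 3. In the most unequal case, with three abstainers at 30 (the eligibility floor, assumed to be on the 0–100 scale) and two others at 100, the fall is 90/290 = 31%.

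With a true abstinence rate of 60%, P(at least 3 of 5) = 0.3456 + 0.2592 + 0.0778 = 0.683. Under the zero rule, that is also the chance of passing both milestones with no effect on the target.

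For a separate pre-quit score, assume an SD of individual percentage change of 20–30 points, independence from abstinence, and a group-mean rule. The standard error is 20/√5 = 8.9 to 30/√5 = 13.4. With a true fall of 0, P(mean fall ≥ 30%) is 0.0004–0.013; times 0.683, this is 0.03–0.9%.

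**4. Relaxing one condition.** The CO sample comes about 6 days before the end-of-treatment visit (36 − 30). Let a share *s* of those abstinent at 24 hours still be smoke-free then. A mean fall of 30% needs at least 2 zeros of 5.

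- *s* = 0.3: 0.3456 × 0.216 + 0.2592 × 0.348 + 0.0778 × 0.472 = 0.20.
- *s* = 0.7: 0.3456 × 0.784 + 0.2592 × 0.916 + 0.0778 × 0.969 = 0.58.

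If instead 3 of 5 individuals must each reach 30%, the same sums with at least 3 zeros give 0.04 and 0.35.

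**5. The diary itself.** Before the quit date only the practice-quitting module schedules abstinence, and only whole smoke-free diary days could score 0. With *k* such nights of 22 (29 − 7), the smallest true fall that passes is 1 − 0.70/(1 − *k*/22): 26.7% for *k* = 1 and 23.0% for *k* = 2, instead of 30%. Practice quits are described as brief, so *k* may be 0, and then there is no effect.

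**The case for a change.** The strongest case for a change is that the text and Table 2 do conflict, that the diary's content is never listed, and that with five people per module the choice of score can change the result. Even without zeros, an open choice of source helps weak components. At a true fall of 20%, with the SDs above and a correlation of 0.3–0.7 between sources, one named source passes 13–23% of the time and either source 20–37%. A sentence would settle it at little cost.

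The conflict and the unnamed window stand. The inference about harm is weaker. The term change scores might suggest a simple before-and-after difference, but the same sentence goes on to specify how change is examined, and that method cannot be run on one post-quit score. The either-source figures suppose that the team would accept whichever source passes, which nothing in the protocol suggests. The 68% is a chance of meeting the two milestones; it is not a chance of selection, because the d rule also decides.

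Asking instead how strongly people felt like smoking would have a real cost. It measures urge, whereas the protocol rests both the items' validity and the 30% threshold on motives. Figures 2 and 3, which show the design and the hypothesized pathway, are not readable here and may already give the timing.

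**Conclusion.** No change to the plan is needed. The mismatch between the end-of-treatment text and Table 2 is clerical, and the missing comparison window is a gap in detail. An analyst following the written Phase 2 analysis would compare baseline-phase diary nights with treatment-phase nights and treat any end-of-treatment score as descriptive. That keeps the target milestone separate from abstinence, apart from any whole smoke-free practice-quit days.

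The 68% against under 1% contrast requires that the end-of-treatment score be the one counted, that abstainers enter 0 for a recall period holding only smoke-free days, and that everyone abstinent at 24 hours remain so to the visit. The protocol states none of these. Varying the last alone, with 30–70% still smoke-free, gives 20–58% on a group mean or 4–35% on a 3-of-5 individual rule. The abstinence milestone is unaffected on any reading. This conclusion rests on the inference that the nightly diary carries the SMQ-R items, which the design and analysis require but no readable passage states.

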#### Measures.

Psychological Factors. Anhedonia will be assessed with the Environmental Reward Observation Scale (EROS), which measures amount of pleasure experienced from daily activities. Anxiety sensitivity will be assessed with the Anxiety Sensitivity Index (ASI-3), a measure of tendency to fear body sensations. Distress intolerance will be assessed with the Distress Tolerance Scale (DTS), which assesses perceived tolerance of negative physical or emotional states.

Smoking-Related Variables. We will administer a Smoking History Questionnaire to assess baseline smoking characteristics. We will administer validated PROMIS measures of nicotine dependence and smoking coping expectancies. We will administer the Cessation Fatigue Scale, a measure of perceived tiredness of

trying to quit smoking. Smoking status will be assessed with timeline follow-back methods, and will be supplemented with an assessment of expired carbon monoxide (CO) at inperson assessment sessions to provide bioverification of smoking status. Lastly, an outside-study treatment review will be conducted to identify any pharmacotherapy or behavioral therapy for smoking cessation received outside of the study.

COPD-Related Variables. We will conduct a chart review to identify participants' most recent sixminute walk test and spirometry (FEV1) values prior to COPD hospitalization. The chart review will also be used to supplement participants' self-report of any hospitalization for COPD at the time of the 3-month follow-up assessment. COPD symptom impact will be assessed with the COPD assessment test (CAT), an 8-item questionnaire measuring the global impact of dyspnea on health status. PROMIS measures will be used to assess task avoidance and emotional response to dyspnea symptoms.

Table 2. Phase 2 Study Measures	idy Measures Timepoint Assesse		
,	Baseline	Treatment Sessions	End-of- treatment
Demographic Questionnaire	X		
Contact Form	X		
Psychological Factors			
Anxiety Sensitivity Index	X		X
Environmental Reward Observation Scale	X		X
Distress Tolerance Scale	X		X
Smoking-Related Measures			
Smoking Motives Questionnaire-Revised	X		
Smoking History Questionnaire	X		
PROMIS-Nicotine Dependence	X		X
PROMIS-Coping Expectancies	X		X
Cessation Fatigue Scale	X		X
Smoking timeline follow-back	X		X
CO assessment	X	X	X
Outside-study treatment review	X	X	X
COPD-Related Measures			
Six-minute walk test	X		
Spirometry (FEV1)	X		
Charlson Comorbidity Index	X		
COPD Assessment Test	X		X
PROMIS- Dyspnea Task Avoidance	X		X
PROMIS- Dyspnea Emotional Response	X		X
Depression and Anxiety Measures			
PROMIS- Depression short form	X		X
PROMIS- Anxiety short form	X		X
Treatment-Related Measures			
Freiberg Mindfulness Inventory	X	X	X
Avoidance and Inflexibility Scale	X	X	X
Behavioral Activation for Depression			
Scale	X	X	X

Depression and Anxiety Symptoms. PROMIS short forms will be used to assess past-7 day depression and anxiety symptoms. 

Treatment Implementation. To assess treatment implementation, participants will complete process measures at each treatment session assessing skill acquisition specific to each module (i.e., Freiberg Mindfulness Inventory,  Avoidance and Inflexibility Scale,  and Behavioral Activation for Depression Scale,  respectively).

Behavioral Target. The behavioral target will be smoking for affect regulation, as measured by 13 items from the Smoking Motives Questionnaire-Revised (SMQ-R).  $^{33,60}$  Items are adapted from a measure of drinking motives and have been validated to assess coping motives across classes of substance use.  $^{32,60,61}$  SMQ-R items can be modified to assess within-subject, state-like motives for use via ecological momentary assessment  $^{62}$  and have demonstrated good internal consistency.  $^{63}$  Further, these items are sensitive to treatment-related change (i.e., reduced as a function of a brief behavioral intervention) $^{64,65}$  and specifically related to reductions in substance use and associated problems, above and beyond non-affective motives.  $^{64,65}$  Responses are scored from 0 (not at all) to 100 (extremely) and averaged to index the overall tendency to smoke for affect regulation. Threshold of clinically-significant change is set at  $\geq 30\%$ , as this change magnitude was associated with substance use outcomes in prior studies.  $^{64,65}$  Specific items which index smoking for distress termination (e.g., "To turn off negative thoughts about myself"), anxiety reduction (e.g., "Because it helped me when I was feeling nervous"), and pleasure enhancement motives (e.g., "To help me feel more positive about things in my life") will be examined separately in follow-up exploratory analyses.

Clinical Endpoint. The clinical endpoint will be achievement of 24-hour smoking abstinence at end-of-treatment, as verified by CO < 5 ppm,  $^{66,67}$  for at least 60% of participants (i.e., 3 of the 5 participants receiving each module), as this is consistent with rates of initial abstinence achieved by established smoking cessation treatments.  $^{68,69}$  We chose this endpoint because it is highly sensitive to treatment effects,  $^{70}$  strongly predictive of long-term abstinence,  $^{69,71}$  and especially relevant for smokers with elevated psychological risk factors who are vulnerable to early lapse.  $^{72,73}$ 

### **Procedures to Minimize Risk**

Throughout the study phases, we will implement procedures to minimize risk to participants. First, the risk of participant distress will be minimized through ongoing training and supervision of study staff to maintain a good working relationship with participants, thoroughly explain all procedures and address participant questions, and consult with the PI, a licensed clinical psychologist, as needed. The PI will respond to all situations of participant distress or worsening of mental health symptoms, and will provide appropriate psychiatric referrals.

Second, participants will be thoroughly debriefed on common symptoms of nicotine withdrawal. In Phases 2-3, these symptoms will be monitored throughout the active treatment phase and coping with nicotine withdrawal symptoms will be addressed in treatment (either through behavioral counseling or provision of self-help smoking cessation materials).

Third, the risk of potential loss of confidentiality will be minimized through supervision of study staff, storage of all private health information on a secure network drive and the use of numeric code identifiers. Only the study staff will have access to the master list of participants' names and codes. [name] will provide oversight of the maintenance of patient confidentiality and will report any breaches of confidentiality to the IRB. All staff with access to the data with have completed Rush University requirements for the responsible conduct of research including Collaborative Institutional Training Initiative (CITI) training.

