Aim 3: Examine effects of psychological risk factor reduction on smoking outcome. Informed by Aim 2, we will conduct a pilot trial in which 62 participants are randomized to the multi-component behavioral treatment (9 weekly sessions) or self-guided treatment (mailing of printed self-help materials). Each participant will make a quit attempt at week 4. The primary outcome is number of days abstinent for 2 weeks post-quit (range = 0-14 days); secondary outcomes are smoking status at 3 months post-quit, COPD functioning, activity avoidance, and depression and anxiety symptoms. **Hypothesis**: Participants in the behavioral treatment vs. self-guided treatment will demonstrate a) greater number of abstinent days, and b) longer latency to smoke during the quit attempt.

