# 15.0 Data Monitoring Plan to Ensure the Safety of Participants:

In collaboration with [name] and co-mentors, [name] has developed a data safety and monitoring plan for this project that is commensurate with the with the risks, nature, size, and complexity of the study. The proposed study has been designated as a minimal risk study by the Rush University IRB, consists of a behavioral intervention only (no medication), and will occur at a single site. Further, pilot trial procedures have been updated to be conducted on a fully remote basis, with all study contacts occurring via phone or online assessment, to facilitate social distancing. Given these study characteristics, a Data Safety Monitoring Board will not be convened. As detailed below, data and safety monitoring for the pilot trial (i.e., Study 3 of the current project) will consist of oversight by the PI, in coordination with the Rush University Institutional

Review Board (IRB). The PI will be assisted by study Co-Investigator, [name], a board-certified Internal Medicine physician and Medical Director of the Rush University Prevention Center.

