Adverse events. Adverse events are defined as any untoward or unfavorable medical occurrence in a human subject, including any abnormal sign (e.g., abnormal physical exam or laboratory finding), symptom, or disease, temporally associated with the subject's participation in the research, whether or not considered related to the subject's participation in the research. At all assessment points (i.e., Days 0, 28, 42, 56, and 120), we will monitor participant reports of adverse events related to: 1) nicotine withdrawal symptoms; 2) COPD symptoms, including COPD exacerbation, defined as an acute worsening of symptoms of COPD requiring new or increased doses of systemic corticosteroids, antibiotics, and/or emergency treatment or hospitalization; 3) utilization of outside study treatment (e.g., smoking cessation, mental health services, pulmonary rehabilitation, and medication use); and 4) any other symptoms participants believe may be related to study participation. Procedures for identifying and reviewing adverse events, including SAEs, are as follows: The research assistant will review each assessment to identify symptoms of moderate or greater severity, indicated by 1) Minnesota Tobacco Withdrawal Scale score > 24, 2) COPD Assessment Test score > 20, 3) any report of acute COPD exacerbation since the prior assessment, and/ or 4) any other symptom identified by participants to be of moderate or greater severity. In all cases of an assessment indicating symptoms of moderate or greater severity, an assessment summary will be emailed to the PI and study Co-I [name] within 24 hours. Drs. [name] and [name] will review the assessment summary and respond within 24 hours to advise on appropriate actions to be taken. Actions may include continuing to monitor symptoms, contacting the participant for further assessment, advising that the participant contacts his or her healthcare provider, or advising that the participant presents to the Emergency Room.

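### Does the listed Phase 3 assessment schedule break the promise to monitor nicotine withdrawal throughout active treatment?

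*Combined protocol and SAP*

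**What the plan says.** Section 4.0, Procedures to Minimize Risk, commits the study to following withdrawal symptoms: "In Phases 2-3, these symptoms will be monitored throughout the active treatment phase". It adds that coping with them will be addressed in treatment, "either through behavioral counseling or provision of self-help smoking cessation materials", so both Phase 3 arms are within its scope.

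Section 1.0, Aim 3, describes the arms as "multi-component behavioral treatment (9 weekly sessions) or self-guided treatment (mailing of printed self-help materials", and sets the quit: "Each participant will make a quit attempt at week 4". The primary outcome counts abstinent days over the 2 weeks after quitting, and smoking status is assessed again 3 months after quitting.

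Section 15.0 supplies the operating detail for the pilot trial. "At all assessment points (i.e., Days 0, 28, 42, 56, and 120), we will monitor participant reports of adverse events"; withdrawal is first on the list of what is followed. "The research assistant will review each assessment to identify symptoms of moderate or greater severity", one criterion being "Minnesota Tobacco Withdrawal Scale score > 24". Flagged assessments go to the PI and a co-investigator within 24 hours, and they respond within a further 24 hours. Pilot procedures are remote, "with all study contacts occurring via phone or online assessment".

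For Phase 2, neither Table 2 nor the measures text in section 4.0 names a withdrawal scale.

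**The concern.** Monitoring throughout a phase suggests something close to continuous, whereas section 15.0 lists five dates. If the quit is on Day 28, the first listed check after it is Day 42, when the primary-outcome window has closed. In the behavioral arm, weekly sessions could fill that interval. In the self-guided arm nothing in the available text does.

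Two things would be at stake. First, a self-guided participant with troublesome withdrawal in those 14 days could not be picked up by the scale until Day 42. With 62 participants this would concern about 31, assuming 1:1 allocation, which is not stated. Second, if staff hear of events at therapy sessions in one arm only, adverse-event counts by arm would partly reflect how often each arm is contacted.

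Phase 2 raises a smaller version of the point: the same commitment covers it, yet no instrument is named, and section 15.0 calls itself a plan for the project while describing its monitoring as being for the pilot trial.

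**Working it through.** The plan gives no figure to reproduce; the check is day arithmetic and a comparison of sections.

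**Inputs.** Listed days 0, 28, 42, 56, 120 (section 15.0, Adverse events). Quit at week 4, a 14-day outcome window, a 3-month follow-up and 9 weekly sessions (section 1.0, Aim 3).

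**Quit day.** It is never stated as a day number. Day 28 fits every anchor:
- 4 × 7 = 28.
- 28 + 14 = 42, the end of the outcome window.
- 120 − 28 = 92 days, about 3.0 months.
- Nine weekly sessions starting on Day 0 end on Day 8 × 7 = 56.

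**Gap after the quit.** With a quit on Day 28 the next listed day is 42, and 42 − 28 = 14 days. With Day 29 it is 13 days. With a quit on Days 22 to 27, Day 28 itself becomes a post-quit check, 6 to 1 days after quitting, and the following check is 14 days later. So the 14-day interval between listed checks is certain; that it begins at the quit is an inference.

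**Mean wait to the next listed check.** For an event at a uniformly random time, mean wait = Σgap² / (2 × Σgap).
- Days 28 to 42, listed checks only: 14² / (2 × 14) = 7.0 days, maximum 14.
- Weekly sessions, if they count as monitoring: 7² / (2 × 7) = 3.5 days, maximum 7. The ratio is 7.0 / 3.5 = 2.
- Taking Days 0 to 56 gives (28² + 14² + 14²) / (2 × 56) = 1,176 / 112 = 10.5 days, three times 3.5. But 784 of the 1,176 comes from the 28 days before the quit, so this is not a measure of post-quit monitoring.

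The 3.5-day figure also credits sessions at which no withdrawal measure is stated.

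**Does the Day 42 scale look back over the gap?** The recall period is not given. Assuming 24 hours, 7 days or 14 days, the uncovered part is 13, 7 or 0 of the 14 days (93%, 50% or 0%). A range that wide settles nothing.

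**Do the sections conflict?** Section 4.0 gives neither a frequency nor an instrument. Section 15.0 gives dates, a scale, a threshold and an escalation route, and four of its five dates run from Day 0 to Day 56. Read together, the second carries out the first by periodic checks. They conflict only if a minimum frequency is added that neither states.

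**Is the self-guided arm otherwise uncontacted?** This cannot be determined. The copy reviewed passes from the overall design to Phase 2 with no Phase 3 procedures, and no Table 3 appears. The overall design calls the comparator minimally enhanced usual care, so the Aim 3 parenthesis need not be a full contact schedule. Section 15.0, Monitoring of Data Quality, mentions a program that tracks when visits or calls are due. None of this proves extra contact, but together it prevents concluding that there is none.

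**Phase 2.** The nightly diary's items are not itemised in section 4.0, so the absence of a named scale does not show that withdrawal goes unrecorded. The remote CO sample on Day 30 or 44 implies a quit on Day 29 or 43, and the end-of-treatment visit follows about 7 days later, near Day 36 or 50.

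**The case for a change.** The strongest case for a change is that a risk-minimization commitment should match the schedule staff will follow, and that aligning the two costs only wording. Section 10.0 itself names withdrawal distress as a risk in Phases 2 and 3. Recall at Day 42, however long, cannot give timely review of something that happened in the first days after quitting. In Phase 2 the quit date is the day after the last session, so all four sessions precede it, and the Interoceptive Exposure module deliberately brings on withdrawal during treatment.

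What stands is that a cross-reference between sections 4.0 and 15.0, with a line on whether section 15.0 covers Phase 2, would be tidier. What does not stand is the step from there to a defect. The argument needs a monitoring frequency the plan never sets, and silence in a text that lacks the Phase 3 procedures.

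The ascertainment argument is sound in principle, but no between-arm comparison of adverse events is stated; section 15.0 asks only for a summary in the annual report. For COPD exacerbations the question covers everything since the previous assessment, so both arms' intervals are captured at common dates. The PI's response to distress and staff reporting of unanticipated problems within 24 hours do not depend on the scale.

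**Conclusion.** The observation is accurate, but it does not amount to an error in the plan. No withdrawal check is listed between Days 28 and 42, and that is probably the fortnight after quitting. The size is one 14-day interval between listed checks, with a mean wait of 7.0 days against 3.5 if weekly sessions count in the other arm.

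This rests on a quit day inferred as Day 28, events spread evenly over time, and no self-guided contacts beyond the listed days. The available text cannot confirm the last of these. The periodic schedule is a fair reading of the general commitment, and in a study designated minimal risk its spacing is an ordinary design choice. The Phase 2 part is an argument from silence.

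Nothing here alters the primary outcome, a stated analysis or a conclusion. Stating the link between the two sections would supply detail that the study team can fill in for itself, so no change is called for.
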